8. SELECTION AND WITHDRAWAL OF SUBJECTS

8.1. Inclusion Criteria for All Cohorts

Each subject must meet all of the following inclusion criteria to be enrolled in the study:

- Able to provide written informed consent
- Adult subjects \geq 18 years
- Disease measurable by RECIST 1.1 criteria using either CT or MRI scan
- ECOG performance status of 0 or 1
- All subjects must have adequate archival tumor sample (slides or archival FFPE block[s] containing tumor that has not been previously irradiated; FFPE blocks are preferred to slides, and newly obtained biopsies are preferred to archived tissue. Refer to the laboratory manual for further instructions). Excepted are subjects who consent to having a fresh tumor biopsy to provide a fresh tumor sample instead of the archival tumor sample.
- Female subjects of childbearing potential must agree to use a highly effective method of birth control during and for 4 weeks after completion of study. Women are considered to be of childbearing potential unless it is documented that they are over the age of 60 OR postmenopausal by history with no menses for 1 year and confirmed by FSH (using local reference ranges) OR have a history of hysterectomy and/or bilateral oophorectomy OR have a history of bilateral tubal ligation. Highly effective methods of birth control include combined hormonal birth control (oral, intravaginal, or transdermal), or progestogen-only hormonal contraception associated with inhibition of ovulation (oral, injectable, or intrauterine), intrauterine devices (IUDs), intrauterine hormone-releasing system, bilateral tubal occlusion, vasectomized partner (provided partner is the sole sexual partner and there has been a medical assessment of surgical success), or sexual abstinence as defined in Section 8.9.1.
- Fertile male subjects must be willing to practice a highly effective method of birth control for the duration of the study and continuing for 4 weeks after the last dose of XmAb18087 or pembrolizumab (when applicable). Highly effective methods of birth control include vasectomy or a condom in combination with double-barrier methods, spermicide, hormonal birth control, or IUD (nonhormonal) used by the woman.
- Able and willing to complete the entire study according to the study schedule

8.2. Additional Inclusion Criteria for Part A and Part B Cohorts:

In addition to the inclusion criteria above, the following criteria are required for Parts A and B safety run-in and expansion cohorts:

Histologically or cytologically confirmed metastatic MCC or locoregional MCC that
has recurred following standard locoregional therapy with surgery and/or radiation
therapy.

Version 1.0 Page 66 of 145

8.3. Additional Inclusion Criteria for Part A Cohorts:

In addition to the inclusion criteria above, the following criteria are required for Part A safety run-in and expansion cohorts:

• Subjects must have progressed on or been ineligible for treatment with anti-PD1 or anti-PDL1 therapy.

8.4. Additional Inclusion Criteria for Part B Cohorts:

In addition to the inclusion criteria above, the following criteria are required for Part B safety run-in and expansion cohorts:

• Subjects must be eligible to receive pembrolizumab as standard of care.

8.5. Additional Inclusion Criteria for Part C Cohorts:

In addition to the inclusion criteria above, the following criteria are required for Part C safety run-in and expansion cohorts:

• Histologically or cytologically confirmed extensive-stage SCLC that has progressed following standard therapies

8.6. Exclusion Criteria for All Cohorts

Subjects who meet any of the following criteria will be excluded from the study:

- History of prior organ or bone marrow transplant
- History of chronic lymphocytic leukemia
- Subjects currently receiving anticancer therapies
- Subjects who have received anticancer therapies within 2 weeks of the start of study drug (including chemotherapy, radiation therapy, immunotherapy, etc.)
- Prior therapy with an agent directed to another stimulatory or coinhibitory T-cell receptor (eg, CTLA4, OX40, CD137) AND were permanently discontinued from that treatment due to an IRAE
- Failure to recover from any IRAE from prior cancer therapy to ≤ Grade 1 (participants with ≤ Grade 2 neuropathy or endocrinopathies controlled by hormone replacement are eligible)
- Failure to recover from any other toxicity (other than immune-related toxicity) from previous anticancer treatment to ≤ Grade 2
- Known active central nervous system metastases and/or carcinomatous meningitis. Subjects with previously treated brain metastases may participate provided they are stable (without evidence of progression by imaging for at least 4 weeks prior to the first dose of trial treatment and any neurologic symptoms have returned to baseline), have no evidence of new or enlarging brain metastases, and are not using steroids for at least 28 days prior to trial treatment.

Version 1.0 Page 67 of 145

- Have a history of (noninfectious) pneumonitis that required steroids or have current pneumonitis (history of radiographically visible but asymptomatic radiation pneumonitis is allowed)
- Platelet count $< 50 \times 10^9/L$
- Absolute neutrophil count $< 1.0 \times 10^9/L$
- AST \geq 3 × upper limit of normal (ULN), or if subject has known liver metastases, AST > 7 × ULN
- ALT \geq 3 × ULN, or if subject has known liver metastases, ALT \geq 7 × ULN
- Estimated creatinine clearance < 50 mL/min calculated by the Cockcroft Gault or Modification of Diet in Renal Disease formulas at screening
- Treatment with immunosuppressive therapy within 28 days of first dose of study drug
- History or evidence of any other clinically unstable/uncontrolled disorder, condition, or disease (including, but not limited to, cardiopulmonary, renal, metabolic, hematologic, or psychiatric) other than their primary malignancy that in the opinion of the Investigator would pose a risk to subject safety or interfere with the study evaluation, procedures, or completion
- Treatment for any serious bacterial, viral, parasitic, or systemic fungal infections within the 30 days prior to study entry
- Active known or suspected COVID-19 disease
- Active known or suspected autoimmune disease (except that subjects are permitted to
 enroll if they have vitiligo; type 1 diabetes mellitus; residual hypothyroidism due to an
 autoimmune condition that is treatable with hormone replacement therapy only;
 psoriasis, atopic dermatitis, or another autoimmune skin condition that is managed
 without systemic therapy; or arthritis that is managed without systemic therapy beyond
 oral acetaminophen and nonsteroidal anti-inflammatory drugs [NSAIDS])
- Positive test for HIV or hepatitis C antibodies
- Positive test for HBsAg or HBcAb (a subject whose HBsAg is negative and HBcAb is positive may be enrolled if an HBV DNA test is negative and either the subject is treated with potent antiviral therapy or is retested for HBsAg and HBV DNA every month)
- Subject is pregnant or breastfeeding, planning to become pregnant, or expecting to conceive or father children while enrolled in the study, up to the end of study (EOS) visit.
- Positive serum pregnancy test (ie, urine human chorionic gonadotropin) at screening

Version 1.0 Page 68 of 145

8.7. Additional Exclusion Criteria for Part B Cohorts: XmAb18087 in Combination with Pembrolizumab

In addition to the exclusion criteria in Section 8.6, subjects will be excluded from Part B safety run-in and expansion cohorts administered XmAb18087 in combination with pembrolizumab if they meet the following criteria:

- Prior treatment with therapeutics directed at anti-programmed cell death 1 (anti-PD1) or anti-programmed cell death ligand 1 (anti-PDL1)
- Have severe hypersensitivity (\geq Grade 3) to pembrolizumab and/or any of its excipients

8.8. Withdrawal of Subjects

Subjects must be withdrawn if the β -HCG pregnancy test is consistent with pregnancy. Before permanent discontinuation, the treatment may be interrupted to confirm the positive pregnancy test. Pregnancy should be reported as described in Section 11.1.4.2.

The Principal Investigator (PI) also has the right to withdraw subjects from the study at his/her discretion for any of the following reasons:

- Disease progression
- Occurrence of an unacceptable serious or non-serious AE
- Failure to return for follow-up
- Uncontrolled intercurrent illness unrelated to the disease under study that renders continuing treatment with XmAb18087 unsafe or regular study visits impossible
- Investigator decision
- Subject decision
- Death
- Administrative reasons

Subjects will be considered to have completed/ended participation in the study at the time that a subsequent anticancer therapy is administered.

Whenever possible, the Sponsor must be notified within 24 hours if a subject is withdrawn from the study. The reason(s) for a subject's discontinuation from the study are to be recorded in the source documents and the subject's electronic case report form (eCRF).

The EOT eCRF must be completed for all subjects who discontinue XmAb18087 permanently.

For subjects who discontinue prematurely, all assessments described for the EOT visit should be performed at the scheduled visit date, if at all possible. If this is not possible, all assessments should be performed as close to the scheduled dates as is practicable. Post-treatment evaluations should be completed no later than 4 weeks after the final administration of XmAb18087 and prior to initiation of a new treatment for malignancy.

Subjects who are withdrawn for any reason may not reenter this study. The Study Sponsor, Xencor, reserves the right to terminate this clinical study at any time and for any reason.

Version 1.0 Page 69 of 145

8.9. Other Subject Restrictions

8.9.1. Avoidance of Pregnancy

Women are considered to be of childbearing potential unless there is a documented reason (ie, postmenopausal by history with no menses for 1 year and confirmed by FSH [using local reference ranges], OR history of hysterectomy, OR history of bilateral tubal ligation, OR history of bilateral oophorectomy).

Women of childbearing potential must have a negative pregnancy test during screening and at Day 1 prior to study drug infusion and must use 1 highly effective method of birth control during the study and for 4 weeks following last dose of XmAb18087 or pembrolizumab (when applicable). Highly effective methods of birth control include combined hormonal birth control (oral, intravaginal, or transdermal), or progestogen-only hormonal contraception associated with inhibition of ovulation (oral, injectable, or intrauterine), IUDs, intrauterine hormone-releasing system, bilateral tubal occlusion, vasectomized partner (provided partner is the sole sexual partner and there has been a medical assessment of surgical success), or sexual abstinence. Sexual abstinence is considered a highly effective method only if defined as refraining from heterosexual intercourse during the entire period of risk associated with the study treatments. Total abstinence is acceptable when this is in line with the preferred and usual lifestyle of the subject. Periodic abstinence (calendar, ovulation, symptothermal, or postovulation methods) and withdrawal are not acceptable methods of contraception. The Investigator is responsible for evaluating the reliability of the subject's ability to maintain sexual abstinence throughout the duration of the clinical trial.

Fertile male subjects must be willing to practice a highly effective method of birth control for the duration of the study and continuing for 4 weeks after the last dose of XmAb18087 or pembrolizumab (when applicable). Highly effective methods of birth control include vasectomy or a condom in combination with double-barrier methods, spermicide, hormonal birth control, or IUD (nonhormonal) used by the woman.

8.9.2. Use in Nursing Women

[figure not shown]
It is unknown whether XmAb18087 or pembrolizumab are excreted in human milk. Since many drugs are excreted in human milk, and because of the potential for serious adverse reactions in the nursing infant, participants who are breastfeeding are not eligible for enrollment.

Version 1.0 Page 70 of 145

9. TREATMENT OF SUBJECTS

9.1. Identity of Study Treatments

XmAb18087 is a humanized bsAb that binds both CD3 and the tumor antigen SSTR2 to recruit cytotoxic T cells that will kill SSTR2⁺ tumor cells. Intravenous Stabilization Solution is a concentrated form of the XmAb18087 buffer that minimizes protein binding to the administration equipment.

Prior to dilution, the vial containing parenteral drug product should be inspected visually. If particulate matter and/or discoloration are noted, drug should not be administered, and the Sponsor should be notified.

Pembrolizumab (Keytruda[®]) is an approved humanized mAb targeting the cell surface antigen PD1. It will be administered at the dose and schedule of 400 mg IV over 30 minutes every 6 weeks. It is supplied as a 100 mg per 4 mL (25 mg/mL) solution in a single-dose vial. Pembrolizumab is provided by sites as standard of care for advanced MCC.

9.2. Concomitant Therapy

All medications (including over-the-counter medications and herbals) and blood products that are administered within the 30 days prior to start of study treatment and throughout a subject's participation in the study until the post-treatment follow-up visit must be recorded in the source document and on the eCRF. Concomitant medications for other medical conditions are permitted as clinically indicated, subject to the specific requirements outlined in Section 7.9.1 and 7.9.2.

9.2.1. Permitted Medications

Subjects who experience CRS should receive aggressive intervention and supportive measures as indicated. These may include, but are not limited to, epinephrine, antihistamines, corticosteroids, IV fluids, vasopressors, oxygen, bronchodilators, diphenhydramine, acetaminophen, and tocilizumab (see Section 11.3.3 or Appendix C for suggested management of infusion reactions, CRS, and neurologic toxicities).

Subjects who experience IRAE after pembrolizumab exposure should receive specific therapy in accordance with the guidelines in Table 18 and/or the NCCN guidelines for management of IRAEs (Appendix E)

In addition to required prophylactic medications, subjects may also receive the following additional therapy during the clinical trial:

Version 1.0 Page 71 of 145

 Antiemetics, antidiarrheals, anticholinergics, antispasmodics, antipyretics, antihistamines, analgesics, antibiotics, antihyperglycemics, and other medications intended to treat symptoms related to cancer, cancer therapy, or concurrent conditions. Other antitumor treatments may not be received.

CONFIDENTIAL

- Antiviral treatments for subjects with a positive HBcAb (and negative HBV DNA test) at screening
- Transfusions of blood products such as red blood cells (RBCs) and platelets, if medically indicated
- Histamine receptor type 2 antagonists, or proton-pump inhibitors for treatment of indigestion, nausea, and/or vomiting
- Multivitamins, provided they be documented on the concomitant medications eCRF.
 No other vitamins or supplements will be permitted during this study without prior notification and approval of the Medical Monitor.

9.2.2. Excluded Medications

Subjects may not concurrently receive other therapeutics for treatment of their malignancy. It is suggested that subjects not receive live prophylactic vaccinations while enrolled in the study.

9.3. Subject Compliance

The Sponsor or its designee will monitor the study according to GCP guidelines. All investigational therapy will be prepared and administered at the study site, and complete records of administration doses, times, durations, and supportive therapies will be kept.

Dosing will be performed by trained, qualified personnel designated by the PI. The date and time of dosing will be documented on each dosing day. Comments will be recorded if there are any deviations from the planned dosing procedures.

9.4. Blinding and Randomization of Study Treatment

No randomization or blinding is required for this open-label trial.

9.5. Procedure for Breaking the Randomization Code

Not applicable.

Version 1.0 Page 72 of 145

10. STUDY DRUG MATERIALS AND MANAGEMENT

[figure not shown]
10.1. XmAb18087

[figure not shown]
As of 27 April 2020, XmAb18087 has been given to 42 human subjects; hence, the safety profile associated with this agent is not well known and caution should be exercised as infusion reactions, CRS, allergic reactions, or other unexpected reactions may occur.

10.1.1. Pretreatment of XmAb18087

Because administration of XmAb18087 has been associated with nausea and vomiting and has also been associated with symptoms of infusion reaction/CRS in subjects and a severe CRS reaction in 1 subject, prophylactic medications are to be administered to all subjects before at least the first

10.1.2. Prophylaxis of Nausea and Vomiting

are recommended for treatment of the symptoms.

Sites may also choose to use other or additional antinausea/vomiting medications for prophylaxis or treatment of symptoms, according to their practice and assessment of the subject's responses.

10.1.3. Prophylaxis of Infusion Reactions/Cytokine Release Syndrome:

It is also required that all subjects receive the following medications before at least the first 4 doses the of study drug:

- a. Acetaminophen (Tylenol®): 650 mg PO once before dosing with XmAb18087
- b. Diphenhydramine (Benadryl®): 50 mg PO once before dosing with XmAb18087
- c. 10 to 20 mg IV dexamethasone (Decadron®) before dosing with XmAb18087

If a subject receives 4 consecutive doses of XmAb18087 without \geq Grade 1 infusion reaction or CRS, the prophylaxis described above may be modified, including elimination and/or reduced doses of some required medications.

For guidelines on the treatment of infusion reactions and CRS, see Section 11.2 or Appendix C of this protocol.

If at all possible, infusions of XmAb18087 should start before 2 PM local time. This is especially important for the C1D1 and any first dose at an escalated level to ensure that adequate staffing and services are available to manage a severe episode of CRS. In addition, either a Principal

Version 1.0 Page 73 of 145

Protocol XmAb18087-02

Investigator or subinvestigator (MD) must be readily available during, and for a minimum of 24 hours after, administration of an XmAb18087 dose.

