7. INVESTIGATIONAL PLAN

7.1. Overall Study Design and Plan

This is a Phase 1b/2, multiple-dose study of XmAb18087, both as a monotherapy and in combination with pembrolizumab in MCC subjects, and as monotherapy only in SCLC subjects. The study is designed in 3 parts, Part A, Part B, and Part C shown in Figure 4.

Figure 4: Study Design

MCC = Merkel cell carcinoma; PD1 = programmed cell death protein 1; PDL1 = programmed cell death ligand 1; SCLC = small cell lung cancer.

Part A is designed to describe safety and efficacy, and to assess PK and immunogenicity of XmAb18087 monotherapy in subjects with advanced MCC. All eligible subjects will have relapsed or refractory disease that has previously been treated with all standard therapies for which they are eligible.

Part A will enroll safety run-in cohorts to confirm the safety and tolerability of XmAb18087 monotherapy administered IV with weekly step-up dosing for 42-day cycles. Additional subjects will then be enrolled into an expansion cohort and will receive XmAb18087 monotherapy using the recommended dose (RD) identified following the safety run-in cohorts.

Part B is designed to describe safety and efficacy, and to assess PK and immunogenicity of XmAb18087 in combination with pembrolizumab in subjects with advanced MCC. All eligible subjects may be treatment naïve or have relapsed or refractory disease after prior treatment; however, subjects who have received prior treatment with anti-PD1 or anti-PDL1 therapeutics will not be eligible to participate in Part B.

Part B will enroll additional safety run-in cohorts to confirm the safety and tolerability of XmAb18087 in combination with pembrolizumab. Subjects will receive step-up IV dosing of XmAb18087 (except for Cohort 1B, in which subjects will receive the same dose level on each

Version 1.0 Page 42 of 145

dosing day) on Days 1, 8, 22, 29, and 36, and IV dosing of pembrolizumab on Day 15 of each 42-day cycle. Additional subjects will be enrolled into an expansion cohort and will receive XmAb18087 plus pembrolizumab combination therapy using the RD identified following the safety run-in.

Enrollment into Part B safety run-in cohorts (starting with Cohort 1B) may begin after the first safety run-in cohort in Part A (Cohort 1A, one dose level higher than Cohort 1B) has completed the first cycle and the regimen has been demonstrated to be tolerable.

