7.4.3. Intrasubject Dose Escalation

Intrasubject dose escalation of XmAb18087 is permitted in the study. The subject must meet the following criteria in order to be eligible for treatment at the higher dose level:

- The subject tolerates his/her dose level of XmAb18087
- The subject meets criteria for continuation of therapy prior to progression (Section 7.4.1)
- All subjects in the safety run-in cohort at the next higher dose level have completed the
 first cycle of treatment, and the SRC has made the decision that the higher dose level
 is tolerable

No dose escalation will be permitted for pembrolizumab.

For MCC subjects, crossover from monotherapy (Part A) to combination therapy (Part B) is not permitted. Subjects in Part B may not escalate more than once.

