7.7. Safety Run-in Cohorts

In each safety run-in cohort, no more than 1 subject will be initiated on treatment with XmAb18087 on any given day.

The planned initial XmAb18087 dose for all cohorts is $0.3 \,\mu\text{g/kg}$. Subsequent doses will then be escalated in steps (except for Cohort 1B, which will use $0.3 \,\mu\text{g/kg}$ for all doses) as indicated in Table 2, Table 3, and Table 4 in an effort to reduce the incidence and severity of CRS.

For all safety run-in cohorts in Part A, Part B, and Part C, the SRC will decide whether to advance to the next higher dose level cohort based on review of all available safety data. For each cohort, 3 subjects will be initially enrolled. If no subject experiences an adverse event of specific concern (AESC, as defined in Section 7.8 below), the SRC will be convened after all 3 subjects have completed one treatment cycle or discontinued treatment, whichever comes first. If 1 of the initial 3 subjects experiences an AESC, 3 additional subjects will be enrolled in that cohort (up to a total of 6 subjects) prior to convening the SRC. If 2 subjects experience an AESC, no additional subjects will be enrolled until the SRC has convened and made a recommendation based on the available safety data. Based on the type and severity of toxicities observed, the SRC may modify the safety run-in scheme (eg, decreases in dose level, smaller escalation steps, or other changes in the regimen), as long as the changes do not significantly affect the risk profile of the study.

If a subject discontinues treatment prior to completion of the first cycle due to an AE, that subject will not be replaced. If a subject discontinues treatment prior to completion of the first cycle for any other reason, an additional subject may be enrolled as a replacement.

Part A will begin by enrolling 3 to 6 subjects in Cohort 1A. After Cohort 1A dosing is demonstrated to be tolerable and is approved by the SRC, Part B will begin by enrolling Cohort 1B, which is one dose level lower than Cohort 1A.

Part C may begin concurrently with Part A.

The safety run-in portion will continue until establishment of an RD for expansion or until the repeated dose level reaches the highest dose planned in this study.

Enrolling additional subjects beyond 142 will require a protocol amendment.

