Cytokine release syndrome, on the other hand, is more likely to occur after the first dose or first escalated dose of drug than after subsequent doses. It may begin somewhat later and is more likely to be associated with hepatic and neurologic complications, including the following:

- Any of the hypersensitivity signs or symptoms listed above
- Aphasia or word-finding difficulty
- Elevated d-dimer and/or hypofibrinogenemia
- Fatigue (asthenia, lethargy, malaise)
- Gait disturbance/dysmetria
- Hallucinations
- Seizures
- Transaminitis and/or hyperbilirubinemia
- Tremor

The Xencor Medical Monitor should be contacted immediately if questions arise concerning the grade and/or treatment of the infusion reaction.

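### Section 10.1.3 lets CRS prophylaxis be relaxed after any 4 reaction-free doses with no dose-level condition, so Cohort 4B's first 4.0 µg/kg dose, or a first higher dose under Section 7.4.3, can be given with reduced or no dexamethasone

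*Protocol*

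**What the plan says.** Protocol Section 10.1.3 makes three premedications compulsory before at least the first 4 doses: acetaminophen 650 mg, diphenhydramine 50 mg and IV dexamethasone 10 to 20 mg. Once a subject has had 4 consecutive XmAb18087 doses with no infusion reaction or CRS of Grade 1 or higher, "the prophylaxis described above may be modified, including elimination and/or reduced doses of some required medications". The condition counts doses and does not mention dose level. Section 11.3 and Appendix C repeat the 4-dose rule, and their visible text has no dose-level condition either.

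The same section asks for infusions to start before 2 PM if possible and adds: "This is especially important for the C1D1 and any first dose at an escalated level". The stated reason is staffing for a severe CRS episode. Section 11.3.2 says CRS "is more likely to occur after the first dose or first escalated dose of drug than after subsequent doses". Section 7.7 explains that doses are stepped up "in an effort to reduce the incidence and severity of CRS".

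Section 7.4.3 states: "Intrasubject dose escalation of XmAb18087 is permitted in the study". The subject must tolerate the current level and meet the continuation criteria of Section 7.4.1. In addition, "All subjects in the safety run-in cohort at the next higher dose level have completed the" first cycle, and the Safety Review Committee (SRC) must have judged that level tolerable. None of these conditions concerns prophylaxis.

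**The concern.** The protocol treats a first dose at a higher level as a point of raised CRS risk, yet its relaxation rule ignores dose level. A subject can qualify on low doses and then receive a first higher dose under reduced premedication. Dexamethasone is one of the required drugs that may be cut.

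The rest of the plan makes this look like an oversight. Cohorts 3A and 3C double from 2.0 to 4.0 µg/kg at dose 4, where full prophylaxis is compulsory. Cohort 4B makes the same doubling later, in combination with pembrolizumab, where it is not compulsory. Section 10.1.4 ties its own relaxation (shorter post-infusion observation) partly to infusions at the subject's highest dose, whereas Section 10.1.3 has no such link. At stake is CRS at a late step-up that full premedication might have prevented or softened.

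**Working it through.** **Planned step-ups.** The inputs are the dosing rows of Protocol Tables 2, 3 and 4. Only XmAb18087 infusions are counted, so Day 15 in Part B (pembrolizumab) is left out. A step-up is any dose larger than the one before it.

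| Cohort | XmAb18087 doses in order (µg/kg) | Step-ups at dose number |
|---|---|---|
| 1A, 1C | 0.3, 1.0, then 1.0 | 2 |
| 2A, 2C | 0.3, 1.0, 2.0, then 2.0 | 2, 3 |
| 3A, 3C | 0.3, 1.0, 2.0, 4.0, then 4.0 | 2, 3, 4 |
| 1B | 0.3 throughout | none |
| 2B | 0.3, 1.0, then 1.0 | 2 |
| 3B | 0.3, 1.0, 1.0, 2.0, then 2.0 | 2, 4 |
| 4B | 0.3, 1.0, 1.0, 2.0, 2.0, 2.0, 4.0 | 2, 4, 7 |

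Part A has 1 + 2 + 3 = 6 step-ups, Part C has 6, and Part B has 0 + 1 + 2 + 3 = 6. The total is 18. At or before dose 4 there are 18 − 1 = 17. The exception is Cohort 4B's move from 2.0 to 4.0 µg/kg: 5 doses in Cycle 1, dose 6 on Cycle 2 Day 1, dose 7 on Cycle 2 Day 8. The synopsis lists Day 1 of later cycles at both 2.0 and 4.0 µg/kg. If 4.0 is given on Cycle 2 Day 1, the step falls at dose 6. On either reading it is past dose 4.

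Before dose 7, a 4B subject qualifies for relaxation if doses 1–4, 2–5 or 3–6 were all free of reactions. The highest dose in any of those runs is 2.0 µg/kg.

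**Escalations under Section 7.4.3.** The Section 7.4.1 criteria govern dosing past the first cycle, so escalation comes after Cycle 1. With full Cycle 1 dosing, the first higher dose is at the earliest:

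- Part B: 5 + 1 = dose 6
- Parts A and C: 6 + 1 = dose 7

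One held dose in Cycle 1 would make these dose 5 and dose 6, still past dose 4.

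Section 7.4.3 gives no step-up schedule, so assume the subject moves to the higher cohort's Cycle 2+ dose. There are then 7 possible one-level moves:

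- Parts A and C, 2 each: 1.0 to 2.0 and 2.0 to 4.0 µg/kg
- Part B, 3: 0.3 to 1.0, 1.0 to 2.0 and 2.0 to 4.0 µg/kg

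Six are 2-fold, and one is 1.0 / 0.3 = 3.3-fold.

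**Cohort 1B.** Section 7.1 describes step-up dosing in Part B "except for Cohort 1B, in which subjects will receive the same dose level on each" dosing day. A 1B subject's first escalated dose is therefore the Section 7.4.3 move to 1.0 µg/kg. In the other 9 of the 10 run-in cohorts, the first step-up is at dose 2 and is fully premedicated.

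**What happened.** SAP Section 5.1 reports 2 subjects in Part A, 2 in Part C and none in Part B. Section 7.7 says: "For each cohort, 3 subjects will be initially enrolled". The SRC decides on the next level after that, so with 2 subjects neither Part A nor Part C could open a second cohort, and no Section 7.4.3 escalation could occur.

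**The case against.** The best defence is that this is a considered clinical choice. The authors had escalated doses in view in that very section and answered with start-time and staffing precautions. Relaxation is optional, covers only some of the drugs and needs 4 consecutive doses without even a Grade 1 reaction. Dexamethasone is not named as the drug to drop. Section 7.4.3 adds tolerance of the current level and an SRC decision. A physician available for 24 hours, 4-hour observation, continuous oximetry, and steroids and tocilizumab at hand all remain. Section 5.1.7 expects CRS principally after the first dose and reports mostly low-grade events. The dose rationale in Section 5.3 and nearby text are not visible, so a supporting argument may exist there.

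Much of this stands, and it limits the size of the point. It does not remove the gap. The precautions concern managing CRS once it occurs, and tolerating a lower level under full premedication does not show that a higher level is safe without it.

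Section 11.3.2 can also be read narrowly, as meaning only a subject's first step-up. For Cohort 4B that is dose 2, which is covered. On that reading the remaining case is Cohort 1B, planned at 3 to 6 subjects. The wording in Section 10.1.3, which covers any first dose at an escalated level, favours the broader reading, although it was written for staffing.

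A reader might infer two stronger claims that the documents do not support:

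- **Late step-ups lose an inpatient protection that earlier ones have.** Admission is required only for the first 2 doses, and 8 of the 17 early step-ups (doses 3 and 4 in 2A, 3A, 3B, 4B, 2C and 3C) already fall outside it.
- **The one severe CRS reaction in Section 10.1.1 measures the risk.** Its dose, timing and prophylaxis are not given, so it says nothing about late step-ups.

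**Conclusion.** The point holds for the rule as written. One of 18 planned step-ups, the doubling to 4.0 µg/kg in Cohort 4B, and the 7 possible one-level escalations under Section 7.4.3 fall after the mandatory prophylaxis doses. The protocol can therefore allow a first higher dose with reduced or no dexamethasone, at a step it treats as higher risk.

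By plan, the 4B route could involve 3 to 6 run-in subjects, and up to 30 in the Part B expansion if 4B became the recommended dose. The documents do not say what share would qualify for relaxation. They also give no CRS rate at a late step-up, so the added risk cannot be quantified.

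The result rests on Table 3 for Cohort 4B (the other synopsis reading changes only the dose number), on Section 7.4.1 placing escalation after Cycle 1, and on the visible text of Section 10.1.3 being complete on this rule. It would be wrong to infer that any subject was put at risk: there was no actual effect. The value of the change lies in any reuse of this rule.

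**What to change.** Add one sentence to Section 10.1.3, and align Section 11.3 and Appendix C where they repeat the rule:

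*Full prophylaxis (acetaminophen, diphenhydramine, dexamethasone) is given, or resumed, before the first XmAb18087 infusion at any higher dose level, including Cohort 4B's first 4.0 µg/kg and any escalation under Section 7.4.3.*

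How soon to relax again at the new level can stay a clinical judgement.

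This is a cheap improvement. The downside is one extra full premedication, including one steroid dose, per late step-up in an immunotherapy study. For a 4B subject relaxed right after dose 4, the required full premedications rise from 4 to 5. Under Section 7.4.3 the addition is at most 1 per subject in Part B, where only one escalation is allowed, and at most 2 in Parts A and C, where two levels lie above the first cohort. No new data collection is needed, because Section 9.2 already records all medications on the eCRF.
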